attainment, 3) acceptability (Intrinsic Motivation Inventory – Interest/Enjoyment Subscale¹⁰), and Adverse & Serious Adverse Events (Timed Up-and-Go, Falls Efficacy Scale-International, Frequency of Events). Aim 2 outcomes, to assess effect size, will be average 10-day physical activity counts (ActiGraph monitors^{2, 11}) and self-report disability (Late-Life Function and Disability Index (LLFDI)^{12, 13}). In addition, Baseline descriptive measures include demographics, medications, cognition (Folstein Mini-Mental State Exam¹⁴), depression (Geriatric Depression Scale SF^{15, 16}), residual limb quality (Chakrabarty Scale¹⁷), sensory testing (Michigan Neuropathy Screen^{18, 19}), social support (Multidimensional Scale of Perceived Social Support), exercise readiness to change (Exercise Stages of Change^{20, 21}), prosthesis description, and comorbidities (Functional Comorbidity Assessment²²).

[figure not shown]

Fig. 1. Crossover study design.

Interventions and Duration

Thirty-two participants will be randomly assigned to two groups: GROUP1 or GROUP2. The home-based study design is intended to reduce participant burden by removing transportation and time barriers. There will be two participation periods of three months (Months 1-3 and 4-6). PABC intervention will occur Months 1-3 for GROUP1 and Months 4-6 for GROUP2. GROUP2 will participate in a no-exercise, attention control in Months 1-3. GROUP1 will have a no contact, intervention “wash-out” period in Months 4-6.

Evaluations will take place using the following schedule:

Baseline only: At Baseline testing, participants will also complete the following tests/measures/forms:

- 1) Folstein Mini-Mental State Examination
- 2) Geriatric Depression Scale SF
- 3) Chakrabarty scoring of residual-limb quality
- 4) Michigan Neuropathy Screen
- 5) Prosthetic description and Demographic Form
- 6) Functional Comorbidity Index
- 7) Multidimensional Scale of Perceived Social Support

Baseline, 3 and 6 months:

- 1) Timed Up-and-go
- 2) Two Minute Walk Test
- 3) Five Meter Walk
- 4) Single Limb Stance Test
- 5) Falls Efficacy Scale-International
- 6) Activity Measurement
- 7) Self-Efficacy for Exercise Scale
- 8) Intrinsic Motivation Inventory (IMI) – Interest/Enjoyment Subscale
- 9) LLFDI
- 10) Exercise Stages of Change
- 11) Prosthesis Evaluation Questionnaire – Mobility Section

Continuously: Falls, Adverse Events (AEs), and Serious Adverse Events (SAEs) will be recorded and reported as needed.

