We will recruit older Veterans with dysvascular LLA (1-5 years after LLA) to participate in the PABC intervention, which uses established VA Health Care system technology and evidence-based intervention methods. The five key dimensions of feasibility to be assessed are whether Veterans: 1) can successfully participate in the intervention (practicality), 2) tolerate physical activity progression (implementation feasibility), 3) are interested and enjoy the intervention (acceptability), 4) complete the intervention safely (safety), and 5) respond to the intervention with increased activity and decreased disability (responsiveness).^{31,32} Measures of physical activity and disability will be used to establish effect size estimates for the PABC intervention, with the intention of planning a future clinical efficacy trial. Testing will occur at baseline (pre-intervention), three months (end of intervention), and six months, using a two-group randomized crossover design.

Primary Aim: Determine feasibility of using the PABC intervention with older Veterans who have dysvascular LLA by assessing: 1) practicality (measured by retention rate), 2) implementation feasibility (measured by dose goal attainment), 3) participant acceptability (measured by the Intrinsic Motivation Inventory (IMI) – Interest / Enjoyment Subscale), and 4) safety (measured with Adverse and Serious Adverse Events).

Hypothesis 1.1: Retention rate will be at least 85% over the PABC intervention period (i.e., ≤15% attrition).

Hypothesis 1.2: At least 75% of participants will meet the dose goal of a 3% average increase in daily steps per week, across the three months of intervention.

Hypothesis 1.3: Participants will indicate PABC intervention acceptability with a mean score of ≥ 5/7 on the IMI – Interest / Enjoyment Subscale.

Hypothesis 1.4: There will be similar rates of study related (definitely, probably, possibly) adverse events between groups during the first three months (period of direct comparison of intervention versus control).

Secondary Aim: Establish effect size estimates of the PABC intervention (responsiveness)

using physical activity and self-report disability outcomes.

Hypothesis 2.1: The PABC group will have increased activity counts and less self-reported disability than the control group at Month 3, each with effect size estimates ≥ 0.80 (Cohen's d).

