All participants will be recruited from the Denver VA Medical Center (VAMC) or Veterans that are receiving care outside of the VA system in our core-group of regional hospitals. [name] and [name] will use the Amputation Clinic database and meet with the rehabilitation teams to obtain names of Veterans meeting the inclusion criteria. A research team member will then contact the potential participant in person or by letter and ask for permission to explain and complete a brief screening form to determine the Veteran's eligibility. We will increase the recruitment pool for this study from our previous studies, by allowing participants with both transfemoral and transtibial amputation. Recruitment from the Denver VAMC is expected to be feasible based on Denver VAMC data (47 new Veterans seen in rehabilitation for new major LLA in last 18 months).

D.5. Intervention

The home-based study design is intended to reduce participant burden by removing transportation and time barriers. There will be two participation periods of three months (Months 1-3 and 4-6). PABC intervention will occur Months 1-3 for GROUP1 and Months 4-6 for GROUP2 (Fig.1). GROUP2 will participate in a no-exercise, attention control in Months 1-3. GROUP1 will have a no contact, intervention "wash-out" period in Months 4-6.

Study Initiation. A physical therapist will initially meet with the participant at the participant's home to: 1) obtain informed consent and authorization, 2) deliver and orient the participant to wearing an activity monitor (ActiGraph Inc. Pensacola FL), and 3) assess the prosthetic fit and function (Prosthetic Evaluation Questionnaire). If prosthetic fit and function concerns are identified, the participant will be given recommendations for seeing his/her prosthetist, which must be met before beginning the intervention. The participant will wear the ActiGraph monitor for 10 days after the initial visit. The ActiGraph monitor will be used only for outcome data (not intervention) and provides no feedback to participants.

Following the initial visit, participants will be randomized (GROUP1 and GROUP2).

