Each week will include scripted education delivered by the therapist during the video interaction, on a relevant intervention topic (e.g., fall prevention, monitoring blood sugar and diet relative to increasing activity, etc.) (10 minutes). The initial education topic will be fall prevention, to minimize fall risk during the study period.

No-Exercise Attention Control Period. During Months 1-3, GROUP2 will weekly have weekly video interactions with a therapist using the mobile-health tablets, in a no-exercise control period. These meetings will provide health and safety education on non-exercise topics pertaining to older Veterans (e.g., fall prevention, diet, medication management, retirement issues, etc.). Physical activity recommendations will not be discussed. Each week will include scripted education on one topic (10 minutes) and a brief period of light upper and lower extremity range of motion tasks led by the therapist with the video interface and participants seated in a chair (20 minutes). As in the PABC intervention period, the initial education topic for the Control period will be fall prevention, to minimize fall risk during the study period. The rationale for the no-exercise control period is to determine the natural change in physical activity and disability without PABC intervention, while accounting for any potential benefit from contact with the physical therapist (i.e., attention control).

D.6. Outcomes

Outcomes will be measured during in-home visits (Baseline, 3M, and 6M), instead of remotely, to promote safety and reduce fall risk during the test session. Aim 1 outcomes will be 1) participant retention rate, 2) dose goal attainment, 3) acceptability (Intrinsic Motivation Inventory – Interest/Enjoyment Subscale¹⁰), and Adverse & Serious Adverse Events). Aim 2 outcomes, to assess effect size, will be average 10-day physical activity counts (ActiGraph monitors^{2, 11}) and self-report disability (Late-Life Function and Disability Index (LLFDI)^{12, 13}). In addition, Baseline descriptive measures include demographics, medications, cognition (Folstein Mini-Mental State Exam¹⁴), depression (Geriatric Depression Scale SF^{15, 16}), residual limb quality (Chakrabarty Scale¹⁷), sensory testing (Michigan Neuropathy Screen^{18, 19}), exercise readiness to change (Exercise Stages of Change^{20, 21}), prosthesis description, and comorbidities (Functional Comorbidity Assessment²²).

D.7. Data Management

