- H1.1) Retention rate will be assessed using a cut off of 15% attrition (i.e., loss of >6 participants). Mean attrition rate will be compared to the null value of 15% using a one-sample t-test ($\alpha=0.05$). This attrition rate is considered feasible based on previous activity change programs for patients with DM or PAD.^{5, 83}
- H1.2) Dose goal attainment will be assessed by the proportion of participants achieving the goal of 3% average weekly increase in steps, based on activity gains in other intervention studies.^{3, 12, 78} The ability to attain a 3% average weekly step increase for <75% of the participants will be considered a negative result. The proportion of participants attaining a 3% average weekly step increase will be reported (95% CI) and compared to the null value of 75% using a one-sample binomial proportions test ($\alpha=0.05$).
- H1.3) Acceptability of the intervention will be measured with the IMI Interest and Enjoyment subscale, with a mean score of <5/7 considered a negative acceptability result.¹⁰ Mean IMI Interest and Enjoyment score will be compared to the null value of 5.0 using a one-sample t-test ($\alpha=0.05$).
- H1.4) Adverse and serious adverse event (AE/SAE) rates (events/participant) will be compared between groups for Months1-3 (PABC intervention for GROUP1, attention control for GROUP2). We expect similar AE/SAE rates between groups (assessed by Safety Officer and research team).

Aim 2 (Effect Size and Preliminary Efficacy of PABC Intervention): Effect size of the PABC intervention will be calculated with Cohen's d using mean and standard deviation for change in activity counts and LLFDI scores. Statistical inference of group differences for calculation of sample size estimates will be based on linear models with activity counts and LLFDI scores as outcome variables. Explanatory variables in each model will include primary medical diagnosis (PAD, DM, or both), group, and baseline activity count or LLFDI score.

D.10. Expected Outcomes and Interpretation

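### H1.3 has no enjoyment rating from participants who withdraw during PABC, so the mean tested against 5.0 is a mean of those who stayed

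*Combined protocol and SAP*

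**What the plan says.** Section A, Hypothesis 1.3, sets the target: "Participants will indicate PABC intervention acceptability with a mean score of ≥ 5/7 on the IMI" Interest/Enjoyment subscale. Section D.9 (H1.3) gives the analysis, "Mean IMI Interest and Enjoyment score will be compared to the null value of 5.0 using a one-sample t-test", at an alpha of 0.05, "with a mean score of <5/7 considered a negative acceptability result". It names no visit, no analysis set and no rule for a missing score.

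The Synopsis evaluation schedule puts the "Intrinsic Motivation Inventory (IMI) – Interest/Enjoyment Subscale" in the list headed "Baseline, 3 and 6 months", the same calendar dates for both groups. On mode, D.6 says: "Outcomes will be measured during in-home visits (Baseline, 3M, and 6M), instead of remotely". No assessment at withdrawal is described anywhere.

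The groups do not reach the end of treatment together: "PABC intervention will occur Months 1-3 for GROUP1 and Months 4-6 for GROUP2" (D.5). GROUP2 has an attention control in Months 1-3, and GROUP1 has no contact in Months 4-6. Section D puts the number for Aim 1 at 32, both groups together.

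**The concern.** The visit that captures a participant's opinion of PABC is 3M for GROUP1 and 6M for GROUP2. Someone who withdraws from the study before that visit contributes nothing to H1.3. A GROUP2 member who leaves in Months 4-6 may have Baseline and 3M scores, but neither rates PABC.

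Enjoyment is a plausible influence on whether a person stays in a behaviour-change programme. If it is one, the missing ratings are lower on average than those collected, and the mean moves up because dissatisfied people have gone. H1.3 has a fixed pass mark, and D.10 expects the feasibility results to prepare for a larger efficacy study, so an upward bias would mislead the decision the pilot is meant to inform.

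**Working it through.** **Plan's own figures.** The documents give no power, SD or expected mean for the IMI. The power statement in D.8 concerns activity and has no bearing here. The relevant inputs are 32 recruited and at least 26 expected to complete (D.8), the 5.0 mark (D.9), and the two PABC periods (D.5). At 26 completers, losses are 6/32 = 18.75%, against a stated 15% (0.15 × 32 = 4.8 people).

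**Formula.** Let N be the number who start PABC, k the number who withdraw during it unscored, and L the mean score they would have given (assumed). The scored participants must average M = (5N − kL)/(N − k) for the mean over all exposed to equal 5.0.

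**Results with N = 32:**

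| Leavers during PABC (k) | L = 4 | L = 3 | L = 2 | L = 1 |
|---|---|---|---|---|
| 1 | 156/31 = 5.03 | 157/31 = 5.06 | 158/31 = 5.10 | 159/31 = 5.13 |
| 3 | 148/29 = 5.10 | 151/29 = 5.21 | 154/29 = 5.31 | 157/29 = 5.41 |
| 4 | 144/28 = 5.14 | 148/28 = 5.29 | 152/28 = 5.43 | 156/28 = 5.57 |
| 6 | 136/26 = 5.23 | 142/26 = 5.46 | 148/26 = 5.69 | 154/26 = 5.92 |

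**Which losses count.** The six losses the plan allows for are losses from a six-month study, not from PABC. Spread evenly over two groups and two periods (assumed), they are 1.5 per cell:

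- GROUP1, Months 1-3, and GROUP2, Months 4-6: 1.5 + 1.5 = 3 leave during PABC, unscored.
- GROUP2, Months 1-3: 1.5 leave before any PABC, so 32 − 1.5 = 30.5 are exposed.
- GROUP1, Months 4-6: 1.5 leave after their 3M rating.

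Scored: 30.5 − 3 = 27.5. At L = 3, M = (5 × 30.5 − 3 × 3)/27.5 = 143.5/27.5 = 5.22, close to the 5.21 in the table.

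**Illustration with an observed mean of 5.3.** Three leavers at 3: (27.5 × 5.3 + 9)/30.5 = 5.07, still at or above 5. Four of 32 at 3: (28 × 5.3 + 12)/32 = 5.01. Six of 32 at 3: (26 × 5.3 + 18)/32 = 4.87. Only the extreme case crosses the mark.

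**Whether H1.1 would flag it.** Three PABC-period losses are 3/30.5 = 9.8% attrition, inside the 15% limit. Six of 32 is 81.25% retention, which misses the 85% of Hypothesis 1.1 but not the D.9 gloss, which counts only more than six losses as exceeding the limit.

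**The case against.** Several stronger readings are tempting, and the documents do not support them.

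- *Everyone who stops PABC goes unscored.* Visits are set by calendar, and nothing says that stopping PABC cancels them. The gap concerns withdrawal from the study before the end-of-PABC visit.
- *The mean pools Baseline, control-period and wash-out ratings with PABC ratings.* The plan never says so. H1.3 is about PABC, Aim 1 has 32 participants, and a one-sample t-test takes one value per person. One end-of-PABC score each is the natural reading, so naming the visit is a clarification.
- *A passing 5.3 is really a failing 4.87.* That puts all six study losses in the PABC period with a score of 3. The even split above gives 5.07.
- *Retention cannot warn of the problem.* H1.1 is a separate Primary Aim criterion reported beside H1.3, and six losses during PABC would miss its 85% target. At three losses, though, H1.1 is met and gives no warning.

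The other side has three further points. D.11 anticipates falls and complications of DM and PAD, which are reasons to leave unrelated to enjoyment. Losses may also be few: C.3 reports 1 of 23 lost in the team's related trial, which scales to 32/23 = 1.4 people here. And if H1.3 requires the t-test to reject 5.0, the hurdle is already higher: with n = 26 and an assumed SD of 1.0, the observed mean must be about 5.40 (two-sided).

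These limit the size. They do not supply a rating for those who withdraw. At an observed 5.40, three of 32 at 3 gives (29 × 5.40 + 9)/32 = 5.18, but six gives (26 × 5.40 + 18)/32 = 4.95.

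**Conclusion.** The concern holds in a limited form. As planned, H1.3 is estimated without anyone who withdraws during PABC, and the mean is too favourable to the extent that low enjoyment contributes to withdrawal. The documents neither state nor exclude that mechanism.

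On a moderate assumption (three such leavers at 3), those scored need about 5.2 rather than 5.0. The extreme assumption (six at 3) needs 5.46, and a single leaver at 3 needs only 5.06. Leaver scores and the timing of losses are assumptions throughout. This is an inexpensive improvement to a Primary Aim measure, not a flaw that invalidates it.

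**What to change.** In D.6 and D.9:

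1. Define the H1.3 score as one end-of-PABC IMI for each participant who started PABC: 3M for GROUP1, 6M for GROUP2.
2. For anyone withdrawing from the study during PABC, give the same subscale by video or phone at withdrawal and include that score in the mean.
3. Report how many leavers were not scored, with a sensitivity analysis that assigns them low scores, for example the range 1 to 4 used above.

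The stated reason for in-home testing is safety during the test session, which does not apply to a short questionnaire, and the weekly tablet video link already exists (D.5). The cost is protocol wording and one brief contact for a few people. The downsides are a small number of remotely collected ratings after shorter exposure, some refusals, and a reported mean that may be lower. Comparing IMI between GROUP1 and GROUP2 at 3M is optional and not part of this fix.

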The proposed pilot study is a randomized, tester-blinded design assessing PABC intervention feasibility (Aim 1) and effect size (Aim 2). Randomization ($n=32$) will create two groups (GROUP1 or GROUP2) using computer-generated random blocks of 2 and 4, stratified by amputation level (transtibial and transfemoral). An investigator not involved with testing or intervention ([name]) will conceal group allocation. A crossover design is used to simultaneously accomplish the aims and optimize recruitment (Fig.2). The PABC Intervention will be delivered to both groups (GROUP1 during Months 1-3 and GROUP2 during Months 4-6). The crossover design provides $n=32$ for assessing Aims 1 and 2. Intervention effect retention will be tested at six months for GROUP1 ($n=16$).

D.1. Setting

The study will occur at the VA Geriatric Research Education and Clinical Center (GRECC), where Drs. [name] and [name] have dedicated positions ([name] (GRECC Director)). Intervention delivery will occur with the participant at home and therapist at a VA site with access to tablet interface software (e.g. VA Jewell Motion Analysis Lab or VA Clinical Building South, using VA-supplied and approved mobile-health tablets and wearable activity sensors (FitBit)).

D.2. Participants

Thirty-two participants will be recruited from the Denver VAMC. The target sample is older Veterans diagnosed with PAD and/or DM, who have major LLA. We expect $<15\%$ attrition, with a goal of 26 participants completing.

D.3. Eligibility Criteria

Inclusion criteria: ≥ 50 years of age, LLA 1-5 years prior, Type II DM and/or PAD, and

ambulatory without human assistance, in the home or better using a prosthesis, with assistive device as needed, with assistive device as needed. Exclusion criteria: wheelchair as primary form of locomotion, trauma or cancer-related etiology of the LLA, unstable heart condition, uncontrolled hypertension, acute systemic infection, cancer, recent stroke (within 2 years), or lower extremity wound or ulcer that limits ambulation.

D.4. Recruitment Strategies

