The FitBit sensor will be used to guide the intervention and data from the sensors will NOT include personal health information; with generic accounts will be created for each user without participant-identifiable information. FitBit data will not be used as outcomes, but rather, only to guide the PABC intervention. Outcome data will be managed using the REDCap (Research Electronic Data Capture) platform. REDCap is a secure, web-based application designed to support research data capture, providing user-friendly case report forms, real-time data entry validation (e.g., data type and range checks), audit trails, transaction logs, and a de-identified data export to common statistical packages. The VA Eastern Colorado Health Care System has approved REDCap for research use. More detail is provided in the Human Subjects section.

D.8. Sample Size Estimate

The sample size estimate was based on evidence for activity change in patients with DM and PAD, which indicates a reasonable expected increase of 3% walking activity per week (e.g., steps, distance, time) over 3 months.^{3, 12, 77, 78} A baseline mean (SD) of 2000 (900) steps/day was estimated based on data from our ongoing dysvascular LLA RCT (Section C.3.) and published LLA data.^{49, 79, 80} A 3% weekly increase in steps during intervention, assuming no order effect, would provide an effect size of 0.8 (Cohen's d). Based on those assumptions, a sample size of 13 per group with a crossover design (total n=26) provides >95% power to detect an intervention effect (effect size=0.8, $\alpha=0.05$, two-tailed paired t test). The study is generously powered intentionally, because the assumption of 'no order effect' will not likely hold. We will recruit 32 participants, and expect at least 26 to complete. This 15% attrition estimate is conservative, based on an historical attrition rate <15% in our intervention studies with other older adult populations^{81, 82} and our current dysvascular LLA RCT.

D.9. Data Analysis Plan

Aim 1 (Feasibility of PABC Intervention): The analyses for Aim 1 are based on four hypotheses: H1.1) participant retention, H1.2) dose goal attainment, H1.3) intervention acceptability, and H1.4) safety.

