Determining feasibility of the PABC intervention will set the stage for implementing a larger efficacy study. The expected result is that Veterans with LLA can be enrolled and retained in the PABC intervention with adherence to a 3% weekly increase in physical activity dose. In addition, the effect size is expected to be ≥ 0.80 . While similar interventions have been feasible and successful for other chronic disease populations, this trial will be the first to target chronic physical inactivity behavior for Veterans living with dysvascular LLA.

D.11. Participant Safety

Anticipated adverse events include falls and medical complications due to DM and PAD. A Safety Officer ([name]) for the study will meet with the PI quarterly to review study progress and adverse events. [name] is the Outpatient Medical Director for Rehabilitation Services at the Denver VAMC. [name] is also an Associate Professor in the Department of Physical Medicine and Rehabilitation at the University of Colorado. Beyond his clinical expertise, [name] has experience in outcomes research related to patients with LLA and functional exercise interventions. Fall risk will be monitored using the TUG test and Falls Efficacy Scale-International (FES-I) at all test points (baseline, 3M, 6M). Also, occurrence of falls will be recorded at each of weekly visit in both the intervention and control periods. Fall occurrences and other adverse events will be reported on a quarterly basis to the Safety Officer. The incidence of falls, defined as “inadvertently coming to rest on the ground, floor or other lower level, excluding intentional change in position”,⁸⁴ will be of particular focus. All study-related falls (possibly, probably, or definitely) will be tracked. If the total number of falls reaches 4, the Safety Officer will review incidence by group. If the number of falls for the intervention group exceeds that of the control group by 3 (10% of enrollment) at any time, the study will be suspended until an evaluation of study relatedness for each incidence is performed by the Safety Officer.

D.12 Potential Pitfalls and Alternative Strategies

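### H1.4 summarises safety only as events per participant, so with 16 per group one repeat faller can make up the whole group difference, and unequal loss can shift it slightly

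*Combined protocol and SAP*

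**What the plan says.** H1.4 is one of the four hypotheses under the Primary Aim. Section A words it as "There will be similar rates of study related (definitely, probably, possibly) adverse events between groups during the first three months". Section D.9 turns this into a measure: "Adverse and serious adverse event (AE/SAE) rates (events/participant) will be compared between groups for Months1-3". It then leaves the conclusion to judgement: "We expect similar AE/SAE rates between groups (assessed by Safety Officer and research team". H1.1 to H1.3 each name a test and an alpha. H1.4 has no test, margin or confidence interval.

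Three other places bear on the measure:

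- D.11 describes fall recording: "occurrence of falls will be recorded at each of weekly visit in both the intervention and control periods". Its suspension rule also counts falls, not people who fell: "If the number of falls for the intervention group exceeds that of the control group by 3 (10% of enrollment) at any time".
- The Synopsis schedule lists falls, AEs and SAEs as recorded continuously.
- D.8 gives the expected loss: "We will recruit 32 participants, and expect at least 26 to complete". It is not split by group or by three-month period.

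Nowhere do the documents give person-time, a rule for leavers, a definition of the denominator, a count of participants affected, or a way to handle repeat events.

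Section A limits H1.4 to study-related events and D.9 does not. That is a separate matter and does not alter what follows.

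**The concern.** Events per participant is a mean of counts. In a group of 16 it is dominated by anyone with several events, and the protocol gives reason to expect such people. Section C.1 links a Timed Up-and-Go above 19 s to high risk of multiple falls, and reports that 32% of the team's own patients exceeded it at rehabilitation discharge. If that share carried over to this trial (an assumption, since these participants are 1 to 5 years after amputation), 0.32 × 16 ≈ 5 people per group would be at high risk of multiple falls. D.11 names falls as the event of particular focus.

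The ratio also ignores time at risk. Someone who leaves in Month 2 has less opportunity to contribute events than someone who stays, yet may count as one full participant.

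Months 1-3 hold the trial's only randomised comparison of safety between PABC and attention control. The events-per-participant figure is the only summary that the plan gives to those judging similarity, and the results are meant to inform a larger trial.

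**Working it through.** **The plan's own figures.** None is given for H1.4. The only power statement, "a sample size of 13 per group with a crossover design (total n=26) provides >95% power to detect an intervention effect", concerns steps. It reproduces (paired t test, n = 26, d = 0.8, two-sided 0.05: 97.5%) but says nothing about adverse events.

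**Inputs.** 16 per group (section D gives n=16 for GROUP1, and 32 − 16 = 16 for GROUP2). Window of 3 months, so 16 × 3 = 48 person-months per group. Expected loss up to 32 − 26 = 6 over the whole study. Event counts and timing of loss are assumptions, because the documents give none.

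**1. Repeat events.** A participant with e events adds e/16: 3 events add 0.19, 5 add 0.31 and 6 add 0.38. The same person adds 1/16 = 6.25 percentage points to the proportion affected, however large e is. In the scenarios below, one participant has 5 falls and every other affected participant has one event.

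| Scenario | Events per participant, PABC v control | Participants affected, PABC v control |
|---|---|---|
| Faller in PABC, no other events | 5/16 = 0.31 v 0 | 1/16 v 0/16 |
| Faller in PABC, 2 others affected in each group | 7/16 = 0.44 v 2/16 = 0.125 (ratio 3.5) | 3/16 = 19% v 2/16 = 12.5% |
| Faller and 2 others in control, 7 affected in PABC | 7/16 = 0.44 v 7/16 = 0.44 (ratio 1.0) | 7/16 = 44% v 3/16 = 19% |

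The first two rows show one person creating a difference; the third shows one person hiding one. As an illustration only, since no test is planned: 6 falls in one person against none gives an exact Poisson p of 2 × 0.5⁶ = 0.031, while 1/16 against 0/16 gives Fisher p = 1.0. With 2 other events in each group, the same 6 falls give p = 0.11.

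**2. Leavers.** Assume equal true rates, k of 16 lost at mid-period on average (1.5 months lost each), and no events captured after leaving. Time at risk is 48 − 1.5k person-months. With all 16 as denominator the apparent ratio is (48 − 1.5k)/48. With all events divided by completers only, it is (16 − 0.5k)/(16 − k).

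| k lost | All randomised | Completers only |
|---|---|---|
| 2 | 45/48 = 0.94 | 15/14 = 1.07 |
| 3 | 43.5/48 = 0.91 | 14.5/13 = 1.12 |
| 6 | 39/48 = 0.81 | 13/10 = 1.30 |

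Timing matters. If the 2 or 3 leave after about one week, the all-randomised ratios are 14.17/16 = 0.89 and 13.25/16 = 0.83. If both groups lose the same number at the same times, the ratio is 1.0. Dividing by person-months removes the effect in every row.

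**3. Why the interval must allow for clustering.** In simulation with 16 per group and an assumed mean of 0.5 events per participant, an exact Poisson comparison has type I error of 2.8% without clustering. With negative binomial dispersion of 1, 2 and 4 it is 7.0%, 11.3% and 19.0%.

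**The case against.** The strongest reply is that this is a descriptive mean, over one fixed window shared by both groups, in a 32-person pilot. Exposure is nearly equal by design. The Safety Officer should also notice a repeat faller: D.11 calls for review by group at 4 falls, and for evaluation of each fall once the stated excess is reached. Both points stand and limit the severity. They do not change the H1.4 summary, which would still carry that person's falls at full weight.

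A reader might infer more than the documents support, in three ways.

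- **That the measure makes PABC look safer.** PABC asks for daily tablet use and step progression, while control sessions are seated, so unequal loss is conceivable. But both groups have weekly video contact, and no section gives or predicts loss by group. The team's related trial (C.3) had lost 1 of 23. A 13% understatement (0.844/0.969 = 0.871) needs all six expected losses to fall in Months 1-3 and to split 5 to 1. At an assumed 0.5 events per participant (8 per group), 13% is about one event. Even a simple Poisson 95% interval then spans a factor of exp(1.96 × √(1/8 + 1/8)) ≈ 2.7 either way.
- **That leavers necessarily stay in the denominator and stop being observed.** D.9 does not define the denominator. The Synopsis says events are recorded continuously, although it does not say that this continues after withdrawal.
- **That the plan analyses repeat events as independent.** It specifies no test or interval, so it makes no such assumption.

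The remedy has limits too. Person-time does not restrain a repeat faller, and the proportion affected does not correct for shortened follow-up, so both measures are needed. A negative binomial model is fragile here. In simulation at an assumed 0.25 events per participant (dispersion 1 to 2), 25% to 30% of trials had a group without events or a failed fit.

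**Conclusion.** The point holds as a minor weakness with a cheap remedy. Events per participant alone is a poor basis for judging similarity with 16 per group, because one person with 5 falls moves it by 0.31 in either direction. That conclusion needs only the definition in D.9 and the group size.

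The effect of loss is secondary and conditional. It requires unequal loss in Months 1-3, everyone randomised as denominator, and no capture of events after leaving. Under those conditions, with mid-period losses, 2 or 3 of 16 lost makes the rate read 6% to 9% low, which is less than one event if 8 are expected. The group losing more *can* look safer. The documents do not show that it will, or that it would be PABC.

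**What to change.** In D.9, replace the single ratio with wording to this effect:

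*For Months 1-3, each randomised group will be described by (a) the number and percentage of participants with at least one AE or SAE, out of all randomised to that group; and (b) events per person-month, counted from the start of Month 1 to last contact or the end of Month 3, whichever is earlier. The rate ratio will be given with a 95% confidence interval that allows for repeat events within a participant. The judgement of similarity will rest on both measures.*

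The interval could come from a participant-level bootstrap or permutation, or from a robust variance. A negative binomial model should be used only if the event counts support it. If one group has no events, the ratio cannot be usefully estimated, and the counts and person-months should be shown instead.

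The cost is slightly more analysis and an interval that will be wide. No section says that last-contact dates are held, but the weekly sessions in both groups should supply them. No new visit, procedure or participant is needed.
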